11.1. PD Endpoint and Analysis

11.1.1. Endpoint

Absolute and change and percent change from pre-dose baseline of plasma copper concentrations: total copper and PUF copper

11.1.2. Analysis of the Endpoint

Pharmacodynamic analyses will be performed using the PK/PD Sets. For the plasma total copper and PUF copper concentration summaries BLQ values will be set to zero, but no further imputation will be applied to any missing values. For the plasma total copper and PUF copper concentrations, actual values, changes from baseline and percentages change from baseline will be summarized by time point for each treatment.

Mean plasma total copper and PUF copper concentration (absolute and change and percentage change from baseline) versus scheduled time profiles will be presented in figures.

Individual plasma total copper and PUF copper concentration (absolute and change and percentage change from baseline) versus scheduled time profiles will be presented similarly.

Plasma concentrations of total and PUF copper, absolute and change and percentage change from baseline will be presented in a data listing by participant.

Biostatistics summaries of total copper and PUF copper will be repeated for the FAS using the same methods as described above. In these analyses values BLOQ will be set to LLOQ.

This document is confidential.

12. Safety

The population used for safety analyses will be the Safety Set (SS).

Safety analyses will include an analysis of all AEs, ECGs, clinical laboratory data, physical examinations, and vital sign measurements using descriptive statistics.

No inferential statistical analyses are planned on the safety parameters of this study.

12.1. Adverse Events / Adverse Drug Reactions

AEs for all participants in the Safety Set will be included in the AE summaries.

Adverse events will be summarized by system organ class (SOC) and preferred term (PT) for each treatment and overall, based on the MedDRA dictionary version 23.1.

If the relationship to study drug is missing for TEAEs, then the relationship will be counted as related to study product for the summary tables. Missing severity for TEAEs will be counted as Grade 3.

Treatment-emergent AEs are defined as AEs which commence on or after first study drug administration, or those that first occur before first study drug administration but worsen in frequency or severity after first study drug administration.

Treatment/period attribution will be determined by comparing the start date and time of the AE with the actual date and time of dosing. The most recently administered treatment prior to the date and time of onset will be considered as the treatment/period at onset. An AE will only be attributed to the treatment/period when it started, even if it is ongoing over more than one treatment/period.

If the start date of an AE is partially or completely missing, the date will be compared as far as possible with the date of the start of administration of study drug. The AE will be assumed to be treatment-emergent if it cannot be definitively shown that the AE did not occur or increase in severity during the treatment period (worst case approach). The following general rules will be used:

- If the start day is missing but the start month and year are complete, an AE will not be considered as being treatment-emergent only if the start month/year is before the month/year of the first study drug administration.
- If the start day and month are missing but the start year is complete, an AE will not be considered as being treatment-emergent only if the start year is before the year of the first Study Drug administration.
- If the start date is completely missing, an AE will be considered treatment-emergent unless the stop date is before the first study drug administration.

Time since first/last dose will be calculated as the difference between the event start date/time and the date/time of the first/last dose prior to start. Time since first/last dose will be expressed in days, hours and minutes. If time is missing, duration will be calculated as the difference between the start date and dosing date plus 1 and expressed in days. Time since first/last dose and duration will only be calculated when both dates are complete.

This document is confidential.

Duration will be calculated for AEs that resolve as the difference between the resolution date and onset date plus 1 and expressed in days.

The summary tables will include the number of participants and the number of events. Percentages will be based on the number of participants. For summaries by SOC and PT, a participant will be counted once at the SOC level and once at each PT within the SOC level.

For summaries by SOC, PT, and maximum severity, a participant will be counted once at the highest severity level for which the event occurred at the SOC level and the highest severity level for each unique PT within that SOC level. Therefore, participants may only contribute once to each PT and once to each SOC level.

The summaries presenting frequency of AEs by SOC and PT will be ordered by overall descending frequency of SOC and then, within a SOC, by overall descending frequency of PT.

The following tables will be provided:

- An overall summary of the number and percentage of participants reporting TEAEs, serious TEAEs (TESAEs), TEAEs resulting in death, TEAEs leading to withdrawal of study drug, TESAEs leading to withdrawal of study drug, TEAEs by relationship and TEAEs by toxicity grade;
- TEAEs overall by system organ class and preferred term;
- TEAEs by maximum toxicity grade, overall and by system organ class and preferred term;
- TEAEs by toxicity grade, overall and by system organ class and preferred term;
- TEAEs by maximum relationship to study medication, overall and by system organ class and preferred term;
- TEAEs by relationship to study medication, overall and by system organ class and preferred term;
- TEAEs by system organ class sorted by decreasing frequency; TEAEs by preferred term sorted by decreasing frequency;
- Related TEAEs by preferred term sorted by decreasing frequency;
- TESAEs, overall and by system organ class and preferred term;
- TESAEs by maximum relationship to study medication, overall and by system organ class and preferred term;
- TESAEs by relationship to study medication, overall and by system organ class and preferred term;
- Non-serious TEAEs overall and by system organ class and preferred term;
- TEAEs leading to withdrawal of study drug, overall and by system organ class and preferred term;
- TEAEs leading to death, overall and by system organ class and preferred term;

Only TEAEs will be included in the summary tables, however we will generate separate listings for treatment-emergent and non-treatment-emergent AEs. Additional listings will be provided for deaths, serious adverse events, AEs resulting in withdrawal from the study and Adverse Events Leading to Study Drug Withdrawal.

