8.3.1. Time Period and Frequency for Collecting AE and SAE Information

All AEs and SAEs will be collected from the signing of the ICF until the EOS Visit.

All SAEs will be recorded and reported to Alexion or the designee immediately and under no circumstance should this exceed 24 hours, as indicated in Section 10.3. The Investigator will submit any updated SAE data to Alexion within 24 hours of it being available.

Investigators are not obligated to actively seek AE or SAE data after conclusion of the study participation. However, if the Investigator learns of any SAE, including a death, at any time after

a participant has been discharged from the study, and he/she considers the event to be reasonably related to the study intervention or study participation, the Investigator must promptly notify Alexion.

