4.1. Brief Description

[figure not shown]
This is a Phase 1 study to compare the relative bioavailability of 2 formulations of ALXN1840 in healthy participants. Equal doses of the 1.25 mg EC mini-tablet will be compared with a single 15 mg EC tablet (12 × 1.25 mg and 1 × 15 mg, respectively). The study will be conducted in 2 periods. The study will also assess dose-proportionality between 2.5 mg (2 × 1.25 mg), 5 mg (4 × 1.25 mg), 10 mg (8 × 1.25 mg), 15 mg (12 × 1.25 mg), and 30 mg (24 × 1.25 mg) EC minitablen doses in the Dose-Proportionality Extension Period.

The study has a Screening Period (Days -28 to -2), the Two-way Crossover Periods, consisting of 2 dosing periods (Day 1 to Day 11 each), and a Dose-Proportionality Extension Period of 14 days. After completing the Screening Period, enrolled participants will be admitted to the clinical research unit (CRU) on Day -1 for dosing on Day 1 in Dosing Period 1. If discharged after Dosing Period 1, participants will be readmitted to the CRU for Dosing Period 2 following a minimum washout of 14 days after the previous dose, and again for the Dose-Proportionality Extension Period after a minimum washout of 14 days.

This study will be conducted with approximately 48 healthy participants enrolled to allow for a minimum of 40 participants to complete the Dose-Proportionality Extension Period of the study.

The study design is presented in Figure 1 .

Figure 1: Study Design Schematic

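### SAP 12.1's rules for a partly missing AE start date ignore the stop date, so some AEs that ended before the first dose are classed as treatment-emergent

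*SAP*

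**What the plan says.** Events that begin and end before any drug is given can be in the database. Protocol 8.3.1 states: "All AEs and SAEs will be collected from the signing of the ICF until the EOS Visit". SAP 4.1 puts screening on Days -28 to -2, with admission on Day -1.

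SAP 12.1 gives the definition: "Treatment-emergent AEs are defined as AEs which commence on or after first study drug administration". It adds events that began earlier but worsened after that administration. For an incomplete start date it then sets a principle, applied to the time on treatment: "The AE will be assumed to be treatment-emergent if it cannot be definitively shown that the AE did not occur or increase in severity". The SAP calls this a worst-case approach. Three rules follow:

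- Start day missing: "an AE will not be considered as being treatment-emergent only if the start month/year is before the month/year of the first study drug administration".
- Start day and month missing: "an AE will not be considered as being treatment-emergent only if the start year is before the year of the first Study Drug administration".
- Start date wholly missing: "If the start date is completely missing, an AE will be considered treatment-emergent unless the stop date is before the first study drug administration".

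Only treatment-emergent AEs (TEAEs) enter the summary tables. TEAEs and non-treatment-emergent AEs are listed separately.

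**The concern.** A stop date before the first dose proves that the event neither occurred nor worsened on treatment. The principle accepts such proof, and so does the third rule. The first two rules do not. Their *only if* makes an earlier start month or year a necessary condition for leaving TEAE status, so an event that fails this condition stays a TEAE whatever its stop date.

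The ordering is therefore perverse. An event with part of its start date recorded can be a TEAE, while the same event with no start date at all is not. The result also contradicts the TEAE definition at the head of the section. Nothing says whether the principle or the rules prevail, so the choice falls to whoever programs the derivation.

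TEAE incidence is one of the safety endpoints in SAP 5.3. A misclassified event enters the TEAE tables and leaves the listing of non-treatment-emergent AEs.

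**Working it through.** The plan gives no figure on this point, so there is none to reproduce. The check applies the three rules literally.

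**Worked case.** The dates are illustrative, because the documents give no calendar dosing dates. First dose 20 March 2021; AE stopped 12 March 2021, which is 8 days earlier.

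| Recorded start | Rule used | Result as written | Result under the principle |
|---|---|---|---|
| 10 March 2021 | definition | not TEAE | not TEAE |
| March 2021, day missing | first | **TEAE** | not TEAE |
| February 2021, day missing | first | not TEAE | not TEAE |
| 2021, day and month missing | second | **TEAE** | not TEAE |
| 2020, day and month missing | second | not TEAE | not TEAE |
| wholly missing | third | not TEAE | not TEAE |

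The error appears only where the known part of the start date matches that of the first dose.

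**How often the known part matches.** Assume that dosing is equally likely on each day of a 365-day year, that onset is equally likely on each of Days -28 to -1, and that every event stops before dosing. That gives 365 × 28 = 10,220 combinations.

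*Start day missing.* For dosing on day d of a month, min(d − 1, 28) of the 28 onset days fall in the dosing month. Summed over each month:

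- 28-day month: 0 + 1 + … + 27 = 378
- 30-day month: 378 + 28 + 28 = 434
- 31-day month: 434 + 28 = 462

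Year total: 1 × 378 + 4 × 434 + 7 × 462 = 5,348. Share misclassified: 5,348/10,220 = 52.3%. The share depends heavily on the dosing day: 0/28 on the 1st, 4/28 on the 5th, 14/28 on the 15th, 19/28 on the 20th, and 28/28 on the 29th or later.

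*Start day and month missing.* Only onsets in the previous calendar year are excluded. For dosing on 1 to 28 January these number 28 + 27 + … + 1 = 406. Share misclassified: (10,220 − 406)/10,220 = 96.0%.

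*Start date wholly missing.* None misclassified.

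These shares are conditional on the event having a partial start date and having stopped before dosing. They are not expected rates in the trial.

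**Effect on a table.** One added participant among the planned 48 is 1/48 = 2.1 percentage points of overall incidence.

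**After the fix.** With a stop-date exception in the first two rules, 0 of 10,220 are misclassified.

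**The case against.** The strongest reply is that the governing sentence already settles the matter. It assumes treatment emergence only where the contrary cannot be shown, asks for dates to be compared as far as possible, and introduces the three items as general rules. A careful programmer could exclude the worked case on that basis. This correctly identifies the fault as a conflict between a principle and two of its rules, rather than the absence of any rule. It does not remove the fault. The rules are what the section says will be used, and a stop-date test in the third alone suggests that it was left out of the other two on purpose.

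The arguments on size largely stand. The error goes in the direction of the declared worst-case approach. The safety analysis is descriptive, with no inference. The event still appears in an AE listing. It takes a partial start date, a stop date before dosing and a matching month or year, all within a short screening window in a clinic-based study.

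Two stronger readings are tempting and are not supported:

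- A reader might infer that every resolved pre-dose AE with a missing start day or month is miscounted. It is not: starts in an earlier month (first rule) or earlier year (second rule) are correctly excluded.
- A reader might size the effect against an Extension arm of 10 to 12, giving 1/12 = 8.3 to 1/10 = 10 points. That does not follow. The Extension dose comes at least 14 + 14 = 28 days after the first dose, and the event ended before the first. SAP 12.1 attributes an AE to the latest treatment given before onset, so nothing there charges this event to Treatments C to F.

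How to attribute partial-date events to a treatment is a separate missing detail. Any convention for it is debatable, and correcting this error does not require one.

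**Conclusion.** The point holds in limited form. Two of the three date rules in SAP 12.1 contradict the section's own principle and definition. They class an AE that ended before the first dose as treatment-emergent when its known start month and year, or its known start year, are the same as those of the first dose.

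The consequence is minor: a conservative over-count in descriptive tables, of at most about 2 percentage points of overall incidence per affected participant. It is less if that participant already has another TEAE in the same category. This assumes that all 48 planned participants are dosed. The documents do not give the number of partial dates; it is probably small. The 52.3% and 96.0% rest on the uniform-date assumption and show only that the faulty condition is easily met once a date is partial. It remains worth correcting because the written rule gives a demonstrably wrong classification.

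**What to change.** Add one clause to each of the first two rules in SAP 12.1: *or if the AE stop date is before the first study drug administration*. All three rules then apply the same test and agree with the governing principle. Where the stop date is missing, or cannot be placed before the first dose, the worst-case assumption stays in force, so no genuinely uncertain event is lost.

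The cost is two clauses in the SAP and a small change to the AE derivation program. Data collection and the other analyses are unaffected.

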12.2. Laboratory Evaluations

Safety laboratory samples for hematology, chemistry, urinalysis and coagulation will be collected at Screening, Day 1, 2, 5 and 10 of each treatment period and EOS/ET.

Samples for pregnancy test will be collected at Screening, Day -1 of each treatment period and EOS/ET.

This document is confidential.

Samples for alcohol breath test and urine drug screen will be collected at Screening and Day -1 of each treatment period.

Samples for FSH, HIV antibody/hepatitis B and C screen and serum Ceruloplasmin and serum copper will be collected at Screening only.

The following parameters will be included:

Hematology: Platelets, White blood cell count with differential (neutrophils, lymphocytes, monocytes, eosinophils, basophils), Mean cell hemoglobin, Neutrophils, Monocytes, Basophils, Hemoglobin, Mean corpuscular volume, Lymphocytes, Eosinophils.

Clinical chemistry: Blood urea nitrogen, Potassium, Creatinine, Creatine kinase, Sodium, Chloride, Glucose, HbA1c (only at screening), Bicarbonate, AST, Gamma glutamyltransferase, ALT, Alkaline phosphatase, Urea, Magnesium, Total and direct bilirubin, Total protein, Albumin, Calcium, Phosphate.

Urinalysis: Bilirubin, Glucose, Leukocytes, Nitrite, Protein, Urobilinogen, Blood, Ketones, Microscopy, if required, pH, Specific gravity, Red blood cells.

Coagulation: Prothrombin time - International Normalized Ratio, Partial thromboplastin time.

Serology: Human immune deficiency virus (HIV)-1 and HIV-2 antibodies, hepatitis B surface antigen, and anti-hepatitis C virus with confirmation by hepatitis C virus RNA

Highly sensitive serum or urine human chorionic gonadotropin pregnancy test (as needed for women of childbearing potential), Follicle-stimulating hormone (postmenopausal females only)

Alcohol breath and urine drug screen: amphetamines, barbiturates, benzodiazepines, cocaine, opiates, phencyclidine, methamphetamine, 3,4-methylenedioxy-methamphetamine, methadone, and tetrahydrocannabinol [cannabinoids].

Other tests: Serum Ceruloplasmin, serum copper

Laboratory parameter values will be graded according to the National Cancer Institute Common Terminology Criteria for Adverse Events (CTCAE).

All summaries will be based on results in SI (standard international system of units) units and will be output in the order listed above.

Toxicity grading following the NCI CTCAE grades version 5.0 will also be derived for laboratory variables where applicable (see list below). Note, where gradings require investigator/clinical input, this will not be considered and only the numeric criteria will be used for the assignments. If this results in the criteria for more than one grade being met, the highest (worst) CTCAE grade will be assigned. For creatinine only, the criteria based on the upper limit of normal (ULN) will be used (changes compared to the baseline value will not be used), eg, CTCAE defines Grade 1 as $> \text{ULN} - 1.5 \times \text{ULN}$ or $> 1 - 1.5 \times \text{baseline}$. Only the $\text{ULN} - 1.5 \times \text{ULN}$ criterion will be used (and not the baseline criterion).

The following parameters are CTCAE gradable:

- Hematology: Absolute neutrophil count (neutrophil), total leukocytes (Leukocytes), hemoglobin (only do

This document is confidential.

the grading for Anemia, no grading for Hemoglobin increased), platelet count , Lymphocyte

- Coagulation: International normalized ratio
- Chemistry: Alanine aminotransferase albumin, alkaline phosphatase, aspartate aminotransferase, total bilirubin, creatinine, gamma-glutamyl transferase , glucose (only do the grading the Hypoglycemia, no grading for Hyperglycemia), creatine kinase.

Actual values and changes from baseline (screening) in hematology, coagulation, clinical chemistry, urinalysis will be summarized by treatment.

Shift tables for hematology, clinical chemistry and coagulation from baseline CTCAE toxicity for each visit and to the maximum grade on treatment for each parameter will be provided. Participants with both a non-missing baseline and at least one non-missing post-baseline grade will be included in the shift tables. Unscheduled data will be included in the worst case across all scheduled and unscheduled visits after the first dose of study treatment. This means that if there are CTCAE grades derived from both unscheduled and scheduled visits data per test per participant then the highest grade will be summarized.

For non-CTCAE gradable tests, a shift table will be provided showing shifts relative to the normal ranges. This summary of normal range category changes illustrates the number and percentage of participants who fall into specified categories (Decrease to Low, Change to Normal or No Change, Increase to High) by comparing the baseline normal range category to the planned time normal range category and the worst-case normal range category. The worst-case post-baseline row will be used to summarize the participants' overall worst-case normal range category change. The determination of the worst-case takes into account both planned and unscheduled assessments. Only laboratory tests which cannot be graded per CTCAE v. 5.0 specified criteria will be included.

Participants with missing baseline value are to be assumed to have normal baseline value. Worst-case can be either High or Low. If a participant has a Decrease to Low and an Increase to High during the same time interval, then the participant is counted in both the 'Decrease to Low' and 'Increase to High' categories. If a participant was high at baseline and decreases to Low during the time interval, then the participant is counted in the 'Decrease to Low' category. Likewise, if a participant was Low at baseline and increases to High during the time interval, then the participant is counted in the 'Increase to High' category. Participants are only counted in the 'Change to Normal or No Change' category if they are:

- Normal at baseline and have no normal range High and no normal range Low values during the time interval
 - High at baseline and do not change to Low during the time interval
 - Low at baseline and do not change to High during the time interval
- Shift tables by treatment will be produced for these laboratory parameters. These tables will summarize the number of participants with each baseline grade relative to the reference ranges and changes to the worst highest grade assessed post-dose during the study.

All events of ALT $\geq 3 \times$ upper limit of normal (ULN) and bilirubin $\geq 2 \times$ ULN (> 35% direct bilirubin) or ALT $\geq 3 \times$ ULN and international normalized ratio (INR) > 1.5, if INR measured which may indicate severe liver injury (possible Hy's Law), must be reported as an SAE. Liver function results will be presented in a

This document is confidential.

summary table and eDISH (evaluation of drug-induced serious hepatotoxicity) plots.

All laboratory results, as well as CTCAE grades will be included in data listings. Abnormal results for hematology, clinical chemistry, urinalysis and coagulation will be listed separately. Laboratory results for serology, pregnancy tests, FSH, urine drug screen, alcohol breath test, serum Ceruloplasmin and serum copper will be listed only.

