9.4.2. Safety Analyses

All safety analyses will be performed on the Safety Set.

Safety analyses will include an analysis of all AEs, ECGs, clinical laboratory data, physical examinations, and vital sign measurements using descriptive statistics. No inferential statistical analyses are planned on the safety parameters of this study. The incidence of AEs and SAEs will be summarized, by System Organ Class and Preferred Term for each period, treatment and

overall, by relationship to study intervention. Adverse events will also be summarized by period, treatment and overall by severity. Serious AEs and AEs resulting in withdrawal from the study will be listed. Participants having multiple AEs within a category (eg, overall, System Organ Class, Preferred Term) will be counted once in that category. For severity tables, a participant's most severe event within a category will be counted.

Changes from baseline in vital sign measurements and laboratory assessments (eg, chemistry, cell blood count with differential, and urinalysis) will be summarized by period (Two-way Crossover Period and Dose-Proportionality Extension Period) and treatment. Laboratory parameter values will be graded according to the National Cancer Institute Common Terminology Criteria for Adverse Events (CTCAE). Shift tables by treatment will be produced for these laboratory parameters. These tables will summarize the number of participants with each baseline grade relative to the reference ranges and changes to the worst highest grade assessed post-dose during the study.

The ECG parameters will be measured at the specified time points, including heart rate, PR, RR, QRS, QT, and corrected QTcF intervals. The average of the triplicate ECG readings at the time points collected will be calculated, and changes from pretreatment baseline values will be assessed by period and treatment.

All concomitant medications will be coded and summarized using the World Health Organization (WHO) Drug Dictionary.

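### As SAP 12.2 is written, no laboratory shift table can count an upward shift in blood glucose or hemoglobin (minor)

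*SAP*

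**What the plan says.** SAP 12.2 describes two kinds of laboratory shift table.

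- **CTCAE grade table.** The plan promises "Shift tables for hematology, clinical chemistry and coagulation from baseline CTCAE toxicity for each visit and to the maximum grade on treatment". The gradable tests are listed under "The following parameters are CTCAE gradable". Hemoglobin is on that list with a restriction: "the grading for Anemia, no grading for Hemoglobin increased". Glucose is on it with a similar one: "glucose (only do the grading the Hypoglycemia, no grading for Hyperglycemia".
- **Normal-range table.** Its scope is stated twice. It opens with "For non-CTCAE gradable tests, a shift table will be provided showing shifts relative to the normal ranges" and later adds "Only laboratory tests which cannot be graded per CTCAE v. 5.0 specified criteria will be included". Its categories are *Decrease to Low*, *Change to Normal or No Change* and *Increase to High*.

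The section also gives value summaries: "Actual values and changes from baseline (screening) in hematology, coagulation, clinical chemistry, urinalysis will be summarized by treatment". It lists all results and lists abnormal results separately. Protocol 9.4.2 plans CTCAE grading of laboratory values and says "Shift tables by treatment will be produced for these laboratory parameters"; it does not discuss direction.

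**The concern.** The SAP decides by test which shift table a laboratory parameter goes into, but decides by direction what is graded. For a test graded in one direction only, the other direction then has no home. The SAP creates that situation explicitly for two tests, blood glucose and hemoglobin.

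Clinical laboratory results are a named safety endpoint, and the safety analysis is descriptive, so participant counts by treatment are much of what the laboratory tables offer. Safety samples are taken after at least 10 hours of fasting (Protocol 8.2), so a high blood glucose can be interpreted. HbA1c is measured at Screening only and cannot stand in for it after dosing. The extension arms have 10 to 12 participants each. A reader who looks at the shift tables and sees no upward movement in these two tests could take that as a finding, when the tables could not have shown anything else.

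**Working it through.** There is no figure in the plan to reproduce and no arithmetic to do. The check is to apply the rules of SAP 12.2 to the possible changes.

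Inputs, all from SAP 12.2:

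1. Blood glucose and hemoglobin are on the gradable list; only low values receive a grade.
2. The CTCAE table tabulates baseline grade against post-baseline grade, by visit and at the maximum.
3. The normal-range table admits a test only if it cannot be graded.
4. Mean corpuscular volume is measured but is not on the gradable list, so it serves as a comparator.

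Assumptions: a value outside the graded direction counts as grade 0, and a low value is shown as grade 1 for illustration. The SAP does not define grade 0.

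| Test | Change | CTCAE table | Normal-range table |
|---|---|---|---|
| Glucose or hemoglobin | normal to high | grade 0 to 0 | not in table |
| Glucose or hemoglobin | normal to low | grade 0 to 1 | not in table |
| Glucose or hemoglobin | low to high | grade 1 to 0 | not in table |
| Mean corpuscular volume | normal to high | not in table | *Increase to High* |
| Mean corpuscular volume | normal to low | not in table | *Decrease to Low* |
| Mean corpuscular volume | low to high | not in table | *Increase to High* |

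For glucose and hemoglobin, the first row shows an upward shift nowhere, and the third shows it as an improvement in grade. For the comparator, the same changes are counted. If an ungraded high were treated as missing rather than grade 0, the participant might drop out of the CTCAE table, and the shift would still not show.

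Two passages might close the gap, and neither does so clearly. The phrase about tests that cannot be graded could be stretched to an ungraded direction, but the sentence speaks of tests, and the SAP's own list calls these two gradable. The closing shift-table sentences of SAP 12.2, which nearly repeat Protocol 9.4.2 and mention reference ranges, follow the rules for non-gradable tests and name no exception. Urinalysis glucose is a separate test, not on the gradable list, and is not affected.

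**The case against.** The strongest reply is that little is lost. SAP 7.1 defines continuous summaries to include quartiles, minimum and maximum, so an extreme high value appears in the by-treatment maximum. Abnormal results are listed. Clinically significant laboratory abnormalities are recorded as adverse events (Protocol 8.2.4 and 10.3.1), and SAP 12.1 counts those by participant and treatment. The risks in Protocol Table 3 include anemia, which is graded, but neither high glucose nor high hemoglobin, and Protocol 8.3.5 names no adverse events of special interest. Leaving these directions ungraded is also an explicit choice. Finally, SAP 7.1 refers to table shells, which are not part of these documents and may settle the layout.

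Most of this stands, and it sets the severity. It does not close the gap. Declining to grade a direction is a reasonable choice, but it does not explain why that direction is also kept out of the normal-range table. What remains uncounted by treatment is the high value that the investigator did not judge clinically significant, and counting such values is what a shift table is for.

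A reader might also infer that the SAP departs from the protocol without declaring it. The documents do not support that firmly: Protocol 9.4.2 promises grade-based shift tables without addressing direction, and both tests do have a CTCAE table.

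**Conclusion.** The gap is real and minor. As written, every upward shift in blood glucose and hemoglobin is missing from the shift-table counts. This rests on reading the eligibility rule by test, as the text states it, and does not depend on how an ungraded high is coded. The effect is limited to one descriptive safety display; the primary PK analysis, data collection and the detection of individual abnormal values are untouched.

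Three stronger readings should be resisted.

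- A reader might infer that these shifts are counted as no change in both tables. They are not: the tests are absent from the normal-range table, and only the CTCAE table can show them as unchanged.
- A reader might extend the point to other listed tests graded in one direction. That depends on the CTCAE criteria, which the documents do not reproduce; they state a one-direction rule only for these two tests.
- A reader might want an expected number of lost shifts. The documents give no rate of high values, and chance rates would describe noise rather than a drug effect.

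**What to change.** In SAP 12.2, amend both sentences that set the scope of the normal-range shift table: the opening phrase on non-gradable tests and the later sentence that restricts the table to them. Suggested wording: *The normal-range shift table covers tests that are not CTCAE graded and, in addition, the ungraded high direction of blood glucose and hemoglobin, which is counted as Increase to High.* Name only these two directions; a general rule for every ungraded direction could add many rows of little interest. Leave the CTCAE grading and its shift tables unchanged, and bring the table shells into line.

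The cost is two reworded sentences and a few extra rows in a table that is already planned. No new data are needed.
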